4 STUDY DESIGN & METHODS OF DATA COLLECTION

4.1 Study Design

Study design: Molecular epidemiology cohort study

Study site: Central and North West London (CNWL) NHS Foundation Trust Sexual Health Services (SHS). CNWL is one of the largest SHS in London, providing HIV PrEP to ~300 MSM each month, and routine care for ~3,000 MSM living with HIV.

Study population: MSM aged \geq 18 years. Target of 108 participants, with minimum 40 participants living with HIV¹, distributed evenly across three antibiotic exposure groups at enrolment:

- Group A (n=36): recent² and recurrent³ doxycycline STI prophylaxis use.
- Group B (n=36): recent² history of STI treatment with doxycycline.
- Group C (n=36): no recent² use of any antibiotic for any indication.

¹ 40 study places will be ring-fenced for MSM living with HIV, split evenly across the three groups (12-13 per group).

² recent is defined as within last 3 months.

³ recurrent is defined as 2 or more doses taken.

Eligible individuals meeting the criteria for group A and B, will be allocated to group A.

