behaviour and antibiotic exposure (given differences in STI risk, testing, and treatment) are important potential confounders when studying microbiomes in MSM and people living with HIV.[18] It has also been suggested that both macrolides and tetracyclines have greater impacts on gastrointestinal microbiota compared to other antibiotics.[19] Moreover, alterations in gastrointestinal microbiome have been associated with metabolic, mental health and autoimmune diseases.[23,24] An oropharyngeal microbiome study noted that prevalence of select AMR genes ('resistome') was lower in the general population compared to MSM (ratio 0.41(0.26-0.65)), but found no difference when comparing MSM with and without recent antibiotic exposure.[25] This small cross-sectional study did not assess antibiotic STI prophylaxis and was limited by the lack of data on sexual behaviour including oral sex and ano-oral sexual contact.[25] Microbiome disturbances are multifactorial and differences in the gastrointestinal and oropharyngeal microbiota require careful interpretation as findings may be confounded by sexual behaviour and living with HIV.[22,27] Despite this, a systematic review of human gut resistome studies included no discussion on the potential impact of sexual behaviour or HIV. [26]

While the evidence of STI prophylaxis efficacy in MSM is compelling, given the lack of data on AMR, global differences in baseline AMR, and the potential addition of long-term antibiotic prophylaxis as a recommended STI prevention strategy in MSM, further research is required in the UK on the risks associated with STI prophylaxis and methods for monitoring and mitigation, such as enhanced surveillance. This research will provide data to fill important evidence gaps and develop the methodologies for further AMR research and optimised surveillance.

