4.3 Sample Size

Target sample size 108. This assumes an overall prevalence of AMR in the gut of 32.5%.^[19] Under this assumption, the proposed sample size for this study will allow the prevalence of SPEAR, EDGE (Sponsor) number 174194, IRAS 330315, Protocol, 1.1, 16/DEC/2024

AMR genes of interest across all study participants to be estimated with 95% confidence intervals (CI) +/- 8.85%. The prevalence within the groups of 36 will be possible to estimate with 95%CI +/- 15.5%. This precision will be sufficient to inform the feasibility of larger AMR surveillance research and programmes in the same patient population. In each group of 36 participants, it is expected to observe 11 cases of AMR, with 99% probability of observing at least six cases in each subgroup. This will allow piloting all aspects of specimen processing, genome sequencing, data processing and transfer workflows.

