9 DATA ANALYSIS

9.1 Statistical Analysis

The planned statistical analysis is summarised here. The statistical analysis will be fully outlined in a statistical analysis plan (SAP). The SAP will be written by [name] (Chief Investigator) and [name] (Co-Investigator & Statistician). The SAP will be finalised before any analysis takes place. An analysis of baseline samples will be undertaken once all participants have completed Visit 1.

Sample characteristics, STI prophylaxis use, and questionnaire responses will be described using absolute numbers and proportions. A pooled prevalence estimate with 95% CI for AMR genes/gene mutations of interest will be produced. Chi-square tests will be used to evaluate evidence of differences in prevalence between subgroups, although findings will be presented with caution given the relatively small sample size. The association between detection of AMR genes/gene mutations of interest with demographic and sexual history variables will be described and investigated in exploratory univariable analyses.

Descriptive analyses of AMR detection over time within each group will be conducted. If adequate variation within individuals over time, then generalised estimating equations logistic regression will explore trends over time and consistency of AMR detection within each group.

Statistical analyses will be undertaken on the statistical programmes STATA and R.

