9.2 Bioinformatic Analysis

The bioinformatic methodology and analysis is summarised here. The bioinformatic analysis will be fully outlined in a bioinformatic analysis plan (BAP). The BAP will be written by [name] (Chief Investigator) and [name] (Co-Investigator & Bioinformatician).

Bacterial taxonomic profiling will use both de novo assembly and read-mapping approaches. De novo assembly tools (e.g., MEGAHIT, metaSPAdes) will allow evaluation of taxonomy and AMR genetic diversity. Supervised binning methods will group assembled contigs (DNA sequences) by species using tools such as metaBAT, and the PubMLST/metaMLST reference databases which hosts assembled whole genome sequence data from over 480,000 bacterial isolates. Antibiotic resistance databases (e.g., Comprehensive Antibiotic Resistance Database) will be used to identify genes conferring resistance to tetracyclines (e.g., *tet(M)*, *tet(W)*, *tet(Q)*) and other important antibiotic classes (e.g., Macrolides *mphA*, *ermF*).

To mitigate potential assembly problems from low-abundance organisms, read mapping approaches will be undertaken using the pipeline CCMetagen which uses the National Centre for Biotechnology Information (NCBI) database as reference. Computationally intensive analyses will be carried out in a single *in silico* system that archives and integrates bacterial metagenomes and AMR genes with other rich metadata, and can organise and share genomes to allow integrated analyses and modelling.

Genome-wide association study analyses incorporating machine learning will identify core and accessory genome AMR elements (including plasmids) from complex samples. Genomic variation identified will include gene presence and absence; gene orthologs/alleles; insertions/deletions and single nucleotide polymorphisms (SNPs). These will be linked to AMR and other metadata.

Bacterial genera diversity (microbiome profiles) and AMR genes/gene mutations of interest ('resistome' profiles) will be compared between baseline study groups, and over time by use of doxycycline prophylaxis. Exploratory analysis of microbiome profiles by other characteristics including HIV status and sexual history will be undertaken.

This study does not analyse human DNA.

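### HIV status is a recruitment quota and a named potential confounder, but the stated AMR analyses do not stratify by it or report by it

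*Protocol*

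**What the plan says.** **Recruitment.** Section 4.1 has three exposure groups of 36 and a second quota on HIV: "Target of 108 participants, with minimum 40 participants living with HIV". Its footnote adds: "40 study places will be ring-fenced for MSM living with HIV, split evenly across the three groups", which it gives as 12-13 per group. No maximum is stated. Section 7 monitors enrolment so that the HIV target is met, which again concerns only the floor.

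**Rationale.** Section 2 says of gut and oropharyngeal differences that "findings may be confounded by sexual behaviour and living with HIV". The next sentence faults a review of gut resistome studies for not discussing sexual behaviour or HIV.

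**AMR analyses.** Section 9.1 gives a pooled prevalence, chi-square tests between subgroups (not defined there), exploratory univariable associations, and GEE logistic regression for trends within each group. On the associations it says: "The association between detection of AMR genes/gene mutations of interest with demographic and sexual history variables will be described". HIV status is not mentioned in Section 9.1.

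**Microbiome analyses.** Section 9.2 treats microbiome profiles (genera diversity) and resistome profiles (AMR genes and mutations) as two things. It then names HIV for the first only: "Exploratory analysis of microbiome profiles by other characteristics including HIV status and sexual history will be undertaken".

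**The concern.** A factor that is important enough to set a quota on, and that the Background names as a possible confounder, would normally reappear in the analysis of the main laboratory outcome. Here sexual history is carried into the AMR analysis and HIV is not.

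Two things are at stake.

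- **Group comparison.** The even split of the ring-fenced places fixes only a lower bound on each group's HIV share. Recruitment source may differ by group: Section 7 adds online recruitment to fill Group A, while Section 4.1 says the clinic cares for about 3,000 MSM living with HIV. The HIV mix may differ with it, in an unknown direction, and the crude chi-square would not separate that from exposure.
- **Missing output.** More than a third of the sample (40/108 = 37%) is reserved for men living with HIV, but no AMR prevalence in these men is among the stated results.

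**Working it through.** **Inputs from the protocol.** N = 108, groups of 36, and assumed AMR prevalence p = 32.5% (Section 4.3). HIV floor of 40, at 12-13 per group (Section 4.1).

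**Input not in the protocol.** The difference in AMR prevalence by HIV status. I assume 10 to 20 points, with 5 to 30 as the wider range.

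**1. The plan's own precision.** Half-width = 1.96 × √(p(1−p)/n), with p(1−p) = 0.325 × 0.675 = 0.2194.
- n = 108: 8.83 points (stated 8.85).
- n = 36: 15.3 points (stated 15.5).

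Both agree closely enough to use the same formula below.

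**2. The quota.** 3 × 12 = 36 and 3 × 13 = 39, so the stated range cannot reach 40. An even split of 40 is 13, 13 and 14. With 13 reserved, 36 − 13 = 23 places per group are open to men of either status.

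**3. Shift in a crude group difference with no exposure effect.** Shift = (difference in HIV share) × (difference in prevalence by HIV status).

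| Men with HIV in two groups | Gap 10 points | Gap 20 points |
|---|---|---|
| 13/36 v 23/36 | 10/36 × 10 = 2.8 | 10/36 × 20 = 5.6 |
| 13/36 v 30/36 | 17/36 × 10 = 4.7 | 17/36 × 20 = 9.4 |

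Over gaps of 5 to 30 points, 13/36 v 24/36 gives 1.5 to 9.2 points. The extreme of 13/36 v 36/36 gives 3.2 to 19.2.

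**4. Against the precision of the comparison.** For two groups of 36: 1.96 × √(0.2194 × 2/36) = 21.6 points. With an assumed 25% prevalence in men without HIV and 13/36 v 24/36, the chance of a nominally significant pairwise result in the spurious direction rises from 2.5% to 4.7% (gap 10) or 7.8% (gap 20).

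**5. The estimate that is not stated.** At 32.5%:
- 40 men with HIV: ±14.5 points, slightly tighter than one exposure group.
- 68 men without: ±11.1 points.
- Difference: 1.96 × √(0.2194 × (1/40 + 1/68)) = ±18.3 points. Power reaches about 80% only for a gap near 28 points (32.5% v 60.5%: 81.7%).

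**6. Precision of a stratified comparison.** Pool the two HIV strata with Mantel-Haenszel weights w = n₁n₀/(n₁ + n₀). At a common 32.5%, the half-width is 1.96 × √(0.2194/Σw).
- Equal mix (13 v 13 and 23 v 23): Σw = 6.5 + 11.5 = 18, half-width 21.6, the same as the crude comparison.
- Unequal mix (13 v 23 and 23 v 13): Σw = 8.31 + 8.31 = 16.6, half-width 22.5.

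Adjustment therefore costs at most about one point of precision in these cases. A single stratum read alone is uninformative: 13 v 13 gives 1.96 × √(0.2194 × 2/13) = ±36 points, with about four expected cases per cell.

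**The case against.** The strongest reply is that Sections 9.1 and 9.2 are summaries, and a full statistical and bioinformatic plan will follow. Choice of strata and covariates is ordinary content for those plans, so silence here is not in itself an error. That is right as far as it goes. But the protocol is not merely silent. It states a crude test and lists the variables for AMR detection, and the list leaves out its own quota factor.

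Second, the subgroups in Section 9.1 are undefined and could include HIV, and Section 9.2 speaks of linking genomic variation to other metadata. This stands as an ambiguity. Section 4.3 uses the word for the groups of 36, which points towards A/B/C without settling it.

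Third, the primary objective is feasibility, the tests are to be presented with caution, and the associations are exploratory. The ring-fence also secures about a third of each group. All of this limits the consequences.

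A reader might go further and infer any of the following, which the documents do not support.
- *That the reserved places yield no AMR result.* Those men enter the pooled and the group prevalences. Only an HIV-specific estimate is unstated.
- *That HIV mix would drive the group differences.* Large shifts need both strong imbalance and a strong HIV association with AMR, and the protocol quantifies neither.
- *That HIV as a GEE covariate would repair the contrast.* The GEE describes trends within each group, so a fixed HIV term there does not adjust A v B v C.
- *That recruitment should be capped to balance HIV.* This is a debatable trade-off, given a seven-month window and a Group A that needs online recruitment to fill.

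**Conclusion.** The point holds as a mismatch within the protocol. HIV is a quota variable and a named potential confounder, but no stated AMR analysis names it, while a microbiome analysis does. HIV mix can contribute to crude A/B/C differences: about 3 to 6 points at 13/36 v 23/36. This rests on an assumed 10 to 20 point prevalence difference by HIV status and an assumed imbalance. It is small against ±21.6 points, so it does not undermine the study. It still merits correction, because Section 4.3 means these estimates to inform larger surveillance work, where sampling error shrinks and this bias does not.

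The absence of a stated HIV-specific AMR prevalence is the more practical loss, since the reserved 40 places would support one with about the precision the protocol accepts for an exposure group. Separately, and without any assumption, 12-13 per group is incompatible with a minimum of 40.

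**What to change.** **Section 9.1**
- Define the subgroups to be compared.
- Name HIV status among the variables for AMR detection.
- Report AMR-gene prevalence with 95% CI by HIV status, with the difference labelled descriptive.
- Show the HIV mix of each exposure group.
- Accompany or replace the crude A/B/C chi-square with a Cochran-Mantel-Haenszel comparison pooled over the two HIV strata, labelled exploratory. Do not interpret the strata one at a time.

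**Section 9.2**
- Extend the exploratory analysis by HIV status to resistome profiles.

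**Section 4.1**
- Reconcile the per-group range with the minimum of 40.

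**Cost.** The analysis changes are wording and use a variable that the quota already requires at enrolment. Precision is essentially unchanged when the HIV mix is equal, and about one point wider in the unequal case worked above. No change to recruitment procedures is proposed; the quota correction makes the per-group figures agree with the stated total.

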There are concerns about further development of AMR in MSM sexual networks that already have high rates of STIs with AMR. [12] Unregulated use of self-sourced antibiotics is a particular concern. Doxycycline (a tetracycline antibiotic) is needed as first-line treatment for STIs such as chlamydia, syphilis, and *Mycoplasma genitalium*, as well as respiratory, skin, and other infections. Overall, data on AMR associated with doxycycline prophylaxis from trials remains very limited, or focuses on specific organisms (*Staphylococcus aureus*, *Escherichia coli*, and *Neisseria* species); with no clear conclusions on AMR or the impact long-term doxycycline-PEP has on human microbiomes, although further analyses are expected. [3,4,15] In DOXYPEP, tetracycline resistant *N.gonorrhoeae* was higher in the doxycycline-PEP arm (38%) than at baseline (27%) and in the standard of care (SOC) arm (12%). [3] Additionally, although *S. aureus* carriage was lower in the doxycycline-PEP arm, a higher proportion had doxycycline resistance (16%) compared to SOC (8%). [3] In DOXYVAC, there was more high-level tetracycline resistance among incident gonorrhoea infections with resistance in the doxycycline-PEP arm (33.3%) compared to SOC (18.9%). [4]

Beyond standard microbiological approaches, including in the doxycycline-PEP/PrEP RCTs, there are limited data on genetic determinants of AMR in MSM. A study using residual rectal swab samples from MSM attending SHS in London estimated prevalence of the *mphA* gene (conferring azithromycin resistance) at 32.5%, and higher still (41.3%) among MSM with a diagnosed bacterial STI in the preceding 12 months. [19]

Microbiomes

The impact of sexual behaviour and HIV on the gastrointestinal and oropharyngeal microbiota is of increasing interest. [20-22] Several studies identified differences in the gut microbiota between MSM and men who exclusively have sex with women, and sexual

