3.2 Secondary Objectives

- A) To assess feasibility and acceptability of recruiting STI prophylaxis users via sexual health clinics versus online and obtaining appropriate samples.
- B) To evaluate the use of shotgun metagenomic sequencing to identify AMR genes or gene mutations conferring resistance to tetracycline and other relevant antibiotic classes.
- C) To evaluate the use of shotgun metagenomic sequencing to identify bacteria present in the gastrointestinal tract and oropharynx of MSM.
- D) To estimate the prevalence of AMR genes/gene mutations of interest and describe changes over time in the gastrointestinal tract and oropharynx of MSM using and not using STI prophylaxis.
- E) To characterise the gastrointestinal and oropharyngeal microbiomes and describe changes over time in MSM using and not using STI prophylaxis.
- F) To develop the methodology for future AMR research and surveillance in MSM and other relevant population groups.

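### The crude group comparisons in 9.1 and 9.2 mix doxycycline exposure with STI history, because the group definitions set recent treated STI to all of B, none of C and an unknown share of A

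*Protocol*

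**What the plan says.** Section 4.1 forms three groups of 36. Group A has recent and recurrent "doxycycline STI prophylaxis use". Group B has a "recent² history of STI treatment with doxycycline". The third is "Group C (n=36): no recent² use of any antibiotic for any indication". Recent means within 3 months. A man who qualifies for both A and B is placed in A. Section 6.2 excludes anyone who took an antibiotic other than doxycycline in those 3 months.

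Secondary objective D is to estimate the prevalence of resistance genes and to "describe changes over time in the gastrointestinal tract and oropharynx of MSM using and not using STI prophylaxis". Objective E does the same for the microbiome. Section 9.1 plans chi-square tests of prevalence between subgroups and univariable analyses of demographic and sexual history variables. Section 9.2 says that microbiome and resistome profiles "will be compared between baseline study groups, and over time by use of doxycycline prophylaxis".

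On STI history, the AMR part of section 2 reports that carriage of mphA, an azithromycin resistance gene, was 32.5% in men attending London clinics, "and higher still (41.3%) among MSM with a diagnosed bacterial STI in the preceding 12 months". The 32.5% is also the prevalence used for sizing in 4.3. The microbiome part of section 2 lists sexual behaviour and antibiotic exposure, through STI risk, testing and treatment, among the likely confounders. The enrolment targets in 4.1 and 7 are antibiotic group and HIV status only.

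**The concern.** The men not using prophylaxis enter as B or C, and these two groups sit at opposite ends of recent STI treatment by definition. Because other antibiotics are excluded for everyone, no group holds men recently treated for an STI without doxycycline. In B v C, recent treated STI and doxycycline exposure therefore coincide completely, and no analysis can separate them. In A v C the imbalance is one-sided: C has no recently treated men, while A has a share that the protocol neither fixes nor limits. In A v B it runs the other way.

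If STI history goes with higher gene carriage, the crude contrasts will differ to some extent whether or not doxycycline matters. The study is meant to inform decisions on prophylaxis and the methods of later work (Aim; objective F), so the planned comparisons should show how much of a difference goes with STI history.

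**Working it through.** **The plan's own precision.** At p = 0.325 and n = 36, the half-width 1.96 × √(p(1−p)/n) is 15.3 points, or 15.5 with n−1 in place of n. The stated ±15.5% is reproduced. Expected positives per group are 36 × 0.325 = 11.7. No stated figure is wrong; the point is about structure.

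**Recent antibiotic-treated STI, from 4.1 and 6.2.** Group A: some men, share not stated. Group B: all. Group C: none. C may still hold men whose last treated STI was more than 3 months ago.

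**Illustration with no doxycycline effect.** Inputs from section 2: prevalence 0.413 with a past-year bacterial STI and 0.325 overall. The share *s* of the source population with such an STI is not given, so it is assumed at 10%, 30% and 50%. Prevalence without a past-year STI is then p0 = (0.325 − 0.413*s*)/(1 − *s*).

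Set B at 0.413 and C at p0 (no past-year STI in C). Let half of A have STI history, also an assumption, so A = 0.5 × 0.413 + 0.5 × p0. Rejection rates are exact for the uncorrected chi-square test, two-sided 5%, 36 v 36.

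| s | p0 | B − C (points) | B v C rejects | A − C (points) | A v C rejects |
|---|---|---|---|---|---|
| 10% | 0.315 | 9.8 | 14% | 4.9 | 7.6% |
| 30% | 0.287 | 12.6 | 21% | 6.3 | 9.3% |
| 50% | 0.237 | 17.6 | 37% | 8.8 | 13.3% |

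A lies midway between B and C here, so A − B has the same size as A − C with the opposite sign: −4.9, −6.3 and −8.8 points.

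If C instead sits at the clinic average, B − C = 0.413 − 0.325 = 8.8 points, and the test rejects in 12.4% of studies, against 5.4% when both groups are at 0.325. Across these cases B v C spans about 9 to 18 points and A v C about 5 to 9.

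**Precision of a contrast within men with a past-year STI.** At 0.413 in both groups, the 95% half-width of a difference is 1.96 × √(0.413 × 0.587 × (1/n1 + 1/n2)). For 36 v 18 (all of B against half of A, for example) this is 27.9 points. For 36 v 36 it is 22.7.

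**The case against.** The primary objective is feasibility and acceptability. Objectives D and E estimate and describe, the sample size rests on precision, and chi-square results are to be read cautiously. A reader might infer that the study will report STI history as a doxycycline effect. The protocol says no such thing, and that reading is not supported. The stated reason for caution is sample size, however, and confounding does not shrink with more men.

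The largest figures are for B v C, and neither group is defined by prophylaxis use. The contrasts nearer to the objectives are A v C and A v B, where the illustrated distortion is about half as large and depends on an assumed share in A. The gene is mphA and the STI window is 12 months, so carrying the gap over to tetracycline genes and a 3-month window is an assumption. These objections stand and limit what can be claimed about size.

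A reader might also infer that Group C should be re-recruited to a quota of men with a past-year STI. That does not follow. It would bring men with antibiotic-treated STIs 3 to 12 months earlier into the group meant to be unexposed. At *s* = 50%, with half of C having a past-year STI, the B v C gap would be 0.5 × 17.6 = 8.8 points, the same as with C at the clinic average.

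Finally, a stable baseline difference does not by itself create a trend within a person, so the within-group analyses over time are largely untouched. The relevant histories are collected, and the statistical analysis plan, not shown, may already go beyond the crude tests. What remains is that the protocol names the confounder, builds it into the groups and describes only unadjusted and univariable analyses.

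**Conclusion.** The concern holds as a matter of interpretation of the between-group comparisons. It does not touch the primary objective, the precision statements or, for the most part, the analyses of change within groups. Crude B v C cannot distinguish recent STI treatment from doxycycline. Crude A v C and A v B carry a partial imbalance of unknown size.

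The illustrated gaps, about 9 to 18 points for B v C and 5 to 9 for A v C, are not small beside the stated ±15.5% group precision. They rest on four assumptions: the mphA gap applies to the genes of interest, a past-year STI stands in for recent treatment, *s* lies between 10% and 50%, and (for A v C) half of A and none of C has STI history. They show what is possible and are not a forecast for tetracycline genes.

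**What to change.** Leave the groups and enrolment unchanged. In 9.1 and 9.2:

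1. Beside the crude comparisons, present A v C and A v B stratified by, or adjusted for, bacterial STI in the preceding 12 months, taken from the questionnaire and medical records. Label these exploratory and give estimates with 95% CIs.
2. State that B v C cannot separate recent STI treatment from doxycycline exposure and is to be read as descriptive only.

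The cost is some extra analysis and wording, with no added participants, visits or samples. The strata will be small and the intervals wide, about ±28 points at 36 v 18. B will have few or no men without a past-year STI, so A v B is informative mainly among men with one. Some confounding by how recent the STI was will remain, since any antibiotic-treated STI in C is more than 3 months old. The results will show whether a crude difference persists within STI history, but will not settle its cause.

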4.4 Visit Activities and Samples

There are 3 planned visits for this study (see *Section 5 Study Schedule*). All data and samples will be pseudonymised. A unique identifier (participant ID) will be assigned to each participant enrolled in the study. The participant ID will be used for sample labelling and questionnaire completion. All study activities and procedures will be undertaken after eligibility has been confirmed and informed consent has been given (see *Sections 6 Eligibility Criteria* and *8 Consent* for more details).

At each of the study visits the following three steps will be undertaken:

Step 1: Questionnaire

Participants will self-complete an electronic questionnaire. This will be pseudonymised using the participant ID number, and obtain information on demographics, medical history, sexual activity, STI prophylaxis use, any other antibiotic use, and travel. This will be completed on a tablet or computer in a private clinic room with a member of the research team on hand in case of difficulty or queries. Where possible, the questionnaire incorporates validated questions from other research surveys. It will take approximately 15 minutes to complete.

Step 2: Oropharyngeal Swab

An oropharyngeal swab will be collected from participants by the member of the research team conducting the study visit. Prior to collecting each sample, the researcher will ask the participant for consent to proceed. All samples will be taken in a private clinic room. The swabs will be labelled with the date of collection, the participant ID, and a sample ID number.

Step 3: Stool Sample

Participants will be provided with a stool sample collection kit. For Visit 1, the kit will be provided during the study visit or posted to the participant prior to the visit if they have completed e-consent (see *Section 8 Consent*). Kits will include instructions on how to collect a stool sample and gloves for the collection. The researcher will explain the process of stool sample collection to the participant at the study visit or by telephone if collecting prior to the visit.

Participants will be offered a range of options for collecting stool samples:

- **In clinic at study visit:** participants providing stool samples during the study visit will be directed to a toilet to collect their own sample.

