6.2 Exclusion Criteria

- Use of an antibiotic other than doxycycline in the 3 months prior to enrolment
- Currently being treated for an STI with doxycycline
- Use of doxycycline within the prior 3 months for an indication other than STI treatment or STI prevention.

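### Men with both recent doxycycline prophylaxis and a recent doxycycline treatment course are all placed in Group A, so contrasts of Group A with B or C cannot be read as prophylaxis alone

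*Protocol*

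**What the plan says.** Section 4.1 sets three groups of 36 at enrolment:

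- Group A: "recent² and recurrent³ doxycycline STI prophylaxis use", where recent means the last 3 months and recurrent means at least two doses.
- Group B: "recent² history of STI treatment with doxycycline".
- Group C: "no recent² use of any antibiotic for any indication".

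For men who qualify for two groups the rule is: "Eligible individuals meeting the criteria for group A and B, will be allocated to group A".

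Section 6.2 limits the overlap only in part. It excludes men who are "Currently being treated for an STI with doxycycline", but a course completed within the last 3 months does not exclude.

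On analysis, section 9.1 states that "Chi-square tests will be used to evaluate evidence of differences in prevalence between subgroups", and describes the other association analyses as exploratory and univariable. Section 9.2 states that microbiome and resistome profiles "will be compared between baseline study groups, and over time by use of doxycycline prophylaxis". Both sections are summaries that defer to fuller plans, which are not shown.

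The questionnaire at each visit (section 4.4) will "obtain information on demographics, medical history, sexual activity, STI prophylaxis use, any other antibiotic use, and travel".

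**The concern.** The labels look like three distinct exposures, but after the allocation rule they are not. Group A is prophylaxis with or without a recent treatment course. Group B is treatment without recurrent prophylaxis. Group C is neither.

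The second exposure inside Group A is the same antibiotic. Section 6.2 removes men with recent use of any other antibiotic, or of doxycycline for other indications. Doxycycline treatment of an STI is therefore the one competing antibiotic exposure that Group A admits. Section 2 itself names antibiotic exposure, including through STI treatment, as an important potential confounder in microbiome studies of this population.

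At stake is how the group contrasts are read. The research question in section 3 asks about the AMR and microbiome impact of prophylaxis, the aim is to inform clinical and public health decisions, and Objective F is to develop methods for later research. A grouping that mixes two exposures without showing the mixture would be carried into that later work.

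**Working it through.** **1. The plan's own precision figures.** Section 4.3 assumes a prevalence of 32.5% and states half-widths of ±8.85% (n=108) and ±15.5% (n=36). With half-width = 1.96 × √(p(1−p)/n) and p = 0.325:

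- n=108: 1.96 × √(0.219375/108) = 8.83%
- n=36: 1.96 × √(0.219375/36) = 15.30%

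Inverting the formula, 8.85% and 15.5% need 107.6 and 35.1 men, which round up to 108 and 36. The stated figures are reproduced and are not in dispute.

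**2. How the overlap enters each contrast.** Let f be the share of Group A that also had a treatment course, p_P the prevalence in prophylaxis-only men, and d the added prevalence from a treatment course on top of prophylaxis. Then:

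- Group A = (1−f) × p_P + f × (p_P + d) = p_P + f×d
- A − C = (p_P − p_C) + f×d
- A − B = (p_P − p_B) + f×d
- B − C contains no f×d term

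The same shift enters both contrasts that involve A. The analysis over time by prophylaxis use does not remove it, because it classifies men by prophylaxis and not by treatment.

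**3. Size under assumptions.** The documents give neither f nor d.

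| Assumed f | Assumed d | Shift f×d |
|---|---|---|
| 10% | 10 points | 1 point |
| 50% | 20 points | 10 points |

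One illustration can be built from figures in the protocol. Section 2 cites *mphA* prevalence of 32.5% overall and 41.3% in men with a bacterial STI in the preceding 12 months, a gap of 8.8 points. Using 8.8 for d gives 0.9, 2.2, 4.4 and 6.6 points at f = 10%, 25%, 50% and 75%. This is only for scale: *mphA* confers azithromycin resistance, and the gap compares men by STI history, not by doxycycline treatment.

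**4. Against the noise.** The half-width for A versus C, with 36 per group and p = 0.325 in both, is 1.96 × √(2 × 0.219375/36) = 21.6 points.

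**5. Precision after separating the overlap** (same formula, p = 0.325):

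| Overlap | Dual-exposed / prophylaxis-only | Half-widths |
|---|---|---|
| 10% | 4 / 32 | 45.9% / 16.2% |
| 25% | 9 / 27 | 30.6% / 17.7% |
| 50% | 18 / 18 | 21.6% / 21.6% |

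At 30% overlap about 25 prophylaxis-only men remain: 1.96 × √(0.219375/25) = 18.4%.

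**The case against.** The strongest reply is that this belongs to the analysis plans. Sections 9.1 and 9.2 only summarise, nothing in them forbids separating the overlap, and the data to do so are collected. That is fair as far as it goes: the unseen plans may already handle it. But the point does not rest on missing detail. The protocol fixes an allocation rule and fixes comparisons on the resulting labels; followed as written, the two together give contrasts that mix exposures.

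A second reply is that the study does not claim a causal effect. The primary objective is feasibility and acceptability. Objectives D and E are descriptive, and men who use prophylaxis and were also treated properly belong among the users. Section 9.1 promises caution. This stands. A reader might infer that the plan attributes treatment effects to prophylaxis; no passage says that an A-versus-C difference will be read that way.

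Third, a reader might assume that prophylaxis users are likely to have had recent treatment, and that the mixture makes prophylaxis look worse against Group C. The documents support neither step. Section 2 reports large reductions in STIs under prophylaxis (for example RR 0.35), which could lower the overlap; selection of higher-risk men, or treatment before uptake, could raise it. The direction depends on whether a treatment course raises AMR detection beyond prophylaxis with the same drug, and that increment could be small.

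Finally, separating the overlap does not give a clean contrast. That limit is accepted and is carried into the fix.

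**Conclusion.** The point holds in a limited form. Because dual-exposed men are placed in Group A, differences between A and C or between A and B cannot be read as prophylaxis alone. B versus C is unaffected.

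The shift is the overlap share times the added effect of treatment. Both are unknown, so neither its size nor its direction can be stated from the documents. The 1-to-10-point range rests entirely on the assumed 10-50% overlap and 10-20 points, and even its upper end lies within the 21.6-point half-width for A versus C. No stated sample size or precision figure is overturned, and the feasibility objective is untouched. This is a problem of interpretation that can be corrected cheaply before analysis. It does not show that the allocation rule is wrong or that the planned results would be biased against prophylaxis.

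**What to change.** Keep the allocation rule and make the overlap visible:

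1. Flag each Group A participant who also meets the Group B criteria, and report how many there are.
2. Describe the AMR and microbiome results of these men separately from those of the prophylaxis-only men.
3. Repeat A versus B and A versus C without the flagged men as a sensitivity analysis.
4. Use two exposure indicators (prophylaxis, treatment course) in one model only if the dual-exposed cell is large enough. With about 4 men it would be uninformative.

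The cost is one derived variable from exposure data already collected, and one extra analysis. Recruitment and group sizes do not change.

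There are two downsides. Intervals in the prophylaxis-only subset widen, to about ±18% at n=25 against about ±15% at n=36. That subset is also selected for having had no recent doxycycline-treated STI, so it may differ in sexual behaviour, which section 2 names as a potential confounder. The sensitivity analysis should be labelled exploratory.
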